9.5.1.5 Change in metacarpal cortical width at Month 24 relative to baseline

[figure not shown]
Group 1: the change in metacarpal cortical width at Month 12 relative to both baselines will be evaluated using an ANCOVA model with treatment, pooled center, underlying condition treated with GCs and baseline bone age as explanatory variables. The 2-sided 95% confidence intervals in difference in least squares means between zoledronic acid and placebo will be provided.

Group 2: summary statistics will be reported.

9.5.1.6 Reduction in pain from baseline

The reduction in pain from baseline by visit will be evaluated based on whether or not patients have a decrease in their Faces Pain Scale-Revised from baseline. If pain remains the same or worsens from baseline a patient will be classified as '0' and if the pain scale decreased then the patient will be classified as '1'. Whether or not a patient experiences a decrease in pain will be evaluated using a logistic regression model with treatment, pooled center, underlying condition treated with GCs and baseline pain score as explanatory variables.

Regression analysis will be carried out for Group 1 with respect to both the baselines. However the number and percentage of patients with classified status of pain with respect to baseline 2 will be reported for Group 2.

[REDACTED]

[REDACTED]

9.5.1.10 Other analyses

The following Core data for the patients in the extension FAS-1 will be summarized and analyzed similarly at Core visits to give an overall profile during the 24 months core and extension combined period:

- Change in LS-BMD Z-score relative to baseline
- Change in lumbar spine and total body BMC relative to baseline
- Relative change in biochemical markers of bone turnover (Serum NTX, TRAP-5b, BSAP and P1NP)
- Change in metacarpal cortical width relative to baseline

[REDACTED]

Similar analyses will be performed for FAS-2 for the zoledronic acid group.

9.5.2 Safety variables

[figure not shown]
Safety is the primary objective. Analysis of safety variables are described in [Section 9.4](#).

9.5.3 Resource utilization

Not applicable.

[REDACTED]

[REDACTED]

[figure not shown]

9.5.6 Pharmacokinetics

Not applicable.

9.5.7 Pharmacogenetics/pharmacogenomics

Not applicable.

9.5.8 Biomarkers

Biochemical markers of bone turnover are secondary efficacy variables. The analyses are described in [Section 9.5.1.3](#)

9.5.9 PK/PD

Not applicable.

9.6 Sample size calculation

Participation in the Extension study will be available to all patients completing the Core study CZOL446H2337 and also for the patients who were not eligible to be enrolled to the Core study due to clinically significant back pain from vertebral fracture. Approximately 100 patients in total will be enrolled into the Extension study. Patient recruitment in Group 2 will stop once randomization in the Core study is completed.

9.7 Interim analyses

An interim analysis will not be conducted for this study.

10 Ethical considerations

10.1 Regulatory and ethical compliance

This clinical study was designed and shall be implemented, executed and reported in accordance with the ICH Harmonized Tripartite Guidelines for Good Clinical Practice, with applicable local regulations (including European Directive 2001/20/EC, US Code of Federal Regulations Title 21, and Japanese Ministry of Health, Labor, and Welfare), and with the ethical principles laid down in the Declaration of Helsinki.

10.2 Informed consent procedures

Eligible patients may only be included in the study after providing written (witnessed, where required by law or regulation), IRB/IEC-approved informed consent, or, if incapable of doing so, after such consent has been provided by a legally acceptable representative of the patient. In cases where the patient's representative gives consent, the patient should be informed about the study to the extent possible given his/her understanding. If the patient is capable of doing so, he/she should indicate assent by personally signing and dating the written informed consent document or a separate assent form. Informed consent must be obtained before conducting any study-specific procedures (i.e. all of the procedures described in the protocol). The process of obtaining informed consent should be documented in the patient source documents.

Novartis will provide to investigators in a separate document a proposed informed consent form that complies with the ICH GCP guideline and regulatory requirements and is considered appropriate for this study. Any changes to the proposed consent form suggested by the investigator must be agreed to by Novartis before submission to the IRB/IEC and a copy of the approved version must be provided to the Novartis monitor or designee after IRB/IEC approval.

Women of child bearing potential should be informed that taking the study treatment may involve unknown risks to the fetus if pregnancy were to occur during the study and agree that in order to participate in the study they must adhere to the contraception requirement for the duration of the study. If there is any question that the patient will not reliably comply, they should not be entered in the study.

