4.2 Exclusion criteria

1. Patients who demonstrated a major protocol violation in the Core study (Group 1 only)
2. Patients for whom the investigator considers participation in the Extension study is not appropriate (Group 1 only).

(For both groups)

3. Hypocalcaemia and hypophosphatemia: any value (age-matched) below the normal range at Visit 8 or 8 A.
4. Vitamin D deficiency (serum 25-hydroxy vitamin D concentrations < 20 ng/mL or < 50 nmol/L) at Visit 8 for Group 1, Visit 8 A for Group 2.
5. Local serum ionized calcium below the normal range at Visit 9.
6. Renal impairment defined as an estimated GFR < 60 ml/min/1.73 m² based on the Schwartz formula at screening Visit 8 or 8 A (in the case of DMD additional methods may have been recorded in the source documents). Serum creatinine above the normal range at Visit 9 (Group 1) or an increase between Visit 8 A and Visit 9 greater than 0.5 mg/dL (44.2 μ mol/L) for Group 2.
7. Uncontrolled symptoms of cardiac failure or arrhythmia
8. Any prior use of bisphosphonates (other than study drug during the Core study for Group 1 only) or sodium fluoride (doses for osteoporosis not for dental hygiene).
9. Current active hyperparathyroidism or hyper/hypothyroidism or during the Core study.
10. New diagnosis of sarcoidosis currently or during the Core study.
11. New malignancy diagnosis currently or during the Core study.
12. History of hypersensitivity to any of the study drugs or to drugs of similar chemical classes.
13. History of primary bone disease (OI, idiopathic juvenile osteoporosis, rickets/osteomalacia).
14. Female patients of child bearing potential are eligible only if they are: (1) not pregnant/non-lactating; (2) are sexually abstinent or are surgically sterile or (3) if sexually active, must be practicing a medically acceptable form of birth control for greater than 2 months prior to screening visit.

- Females of child bearing potential who are sexually active must agree to continue to practice their birth control during the trial and at least 1 year after completing the trial and must consent to a pregnancy test prior to every dose administration and at the End of Study (EOS) Visit.

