- [For sites where additional safeguards are required only: Female patients of child bearing potential are eligible only if they are not pregnant/non-lactating. Females of child bearing potential must be practicing a medically acceptable form of birth control for greater than 2 months prior to screening visit. At least one and preferable two complementary forms of contraception including a barrier method should be used and be continued throughout the trial and for at least 1 year after completing the trial. They must also consent to a pregnancy test prior to every dose administration and at the EOS visit. An additional supervised urine pregnancy test will be assessed at Visit 11 (Month 15) (See [Section 6.5.5](#)).

No additional exclusions may be applied by the investigator, in order to ensure that the study population will be representative of all eligible patients.

5 Treatment

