5.6 Study completion and discontinuation

5.6.1 Study completion and post-study treatment

A patient will be considered to have completed the study when the patient has completed all the assessments in the last visit planned in the protocol (Visit 15, Month 24).

Continuing care should be provided by investigator and/or referring physician based on patient availability for follow-up. This care may include:

- Alternative therapy may be prescribed at the discretion of the treating physician at Visit 15 (EOS).

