6.5.5 Pregnancy and assessments of fertility

Serum pregnancy tests (β -hCG) will be performed at Visit 8 of the Core study or Screening visit (for Group 2) and at the final visit (Visit 15) of the Extension study. Urine pregnancy tests will be performed at Visit 9 and Visit 12, prior to study drug infusion. The test will be conducted for all female patients of childbearing potential.

[For sites where additional safeguards are required only due to local regulations e.g. UK, Italy, Germany, Sweden & etc.,: an additional supervised urine pregnancy test will be conducted at Visit 11 (Month 15) 90 days after first study drug administration. In case of a positive test, the patient must contact the investigator immediately.]

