7.2.2 SAE reporting

To ensure patient safety, every SAE, regardless of suspected causality, occurring after the patient or parent/legal guardian has provided informed consent and until 30 days after the patient has stopped study participation (defined as time of last dose of study drug taken or last visit whichever is later) must be reported to Novartis within 24 hours of learning of its occurrence. Any SAEs experienced after this 30 day period after the patient has stopped study participation (defined as time of last dose of study drug taken or last visit whichever is later) should only be reported to Novartis if the investigator suspects a causal relationship to the study drug.

All follow-up information for the SAE including information on complications, progression of the initial SAE and recurrent episodes must be reported as follow-up to the original episode within 24 hours of the investigator receiving the follow-up information. An SAE occurring at a different time interval or otherwise considered completely unrelated to a previously reported one should be reported separately as a new event.

Information about all SAEs (*either initial or follow up information*) is collected and recorded on the Serious Adverse Event Report Form; all applicable sections of the form must be completed in order to provide a clinically thorough report. The investigator must assess the relationship of each SAE to *each specific component of study treatment (if study treatment consists of several components)*, complete the SAE Report Form in English, and submit the completed, signed form within 24 hours after awareness of the SAE to the local Novartis Drug Safety and Epidemiology Department specific to the site, and listed in the investigator folder provided to each site. The original copy of the SAE Report Form must be kept with the case report form documentation at the study site.

Follow-up information is submitted as instructed in the investigator folder. Each re-occurrence, complication, or progression of the original event must be reported as a follow-up to that event regardless of when it occurs. The follow-up information should describe whether the event has resolved or continues, if and how it was treated and whether the patient continued or withdrew from study participation.

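### Section 10.2 limits the fetal-risk information and the contraception agreement to the study itself, although Section 4.2 requires contraception for at least one further year

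*Protocol*

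**What the plan says.** Section 10.2 of the protocol (informed consent procedures) has three elements on this subject.

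- Information: women of child-bearing potential are to be told that treatment may carry unknown fetal risks should they become pregnant while in the study.
- Agreement: they are to "agree that in order to participate in the study they must adhere to the contraception requirement for the duration of the study".
- Entry judgement: "If there is any question that the patient will not reliably comply, they should not be entered in the study".

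Section 4.2, exclusion criterion 14, sets the contraception rule in two variants.

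- Standard sites: sexually active girls of child-bearing potential "must agree to continue to practice their birth control during the trial and at least 1 year after completing the trial".
- Sites where additional safeguards are required: girls of child-bearing potential must use contraception, which is to "be continued throughout the trial and for at least 1 year after completing the trial".

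Section 5.6.1 treats a patient as having completed the study once the Visit 15 assessments are done. Section 10.2 adds that the sponsor will give investigators "in a separate document a proposed informed consent form". The SAP does not address the matter.

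**The concern.** Section 10.2 is where the protocol tells investigators what a girl must be told and must agree to. On its wording, both end with the study. Section 4.2 makes a commitment at least a year longer a condition of entry. Both are current text, and nothing in the protocol reconciles them or says which prevails.

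The entry judgement makes this more than a loose phrase. An investigator who follows Section 10.2 asks whether a girl will reliably use contraception until Visit 15. Under Section 4.2 the question is whether she will do so for at least another year. A girl could be thought reliable for the first period and not for the second.

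The contraception rule has a stated reason. Section 3.6 reports teratogenicity in the rat, though not the rabbit, and bases the requirement on the animal reproduction studies. The year after completion rests on what the girl has understood and agreed to, so the section on consent ought to state it.

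**Working it through.** No figure in the plan needs reproducing. The check is a comparison of the texts and a short count of days.

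**Who is covered.** Section 10.2 speaks of all women of child-bearing potential. In Section 4.2 the further year applies to sexually active girls at standard sites and to girls of child-bearing potential at sites with additional safeguards. Girls at standard sites who are eligible through abstinence or surgical sterility are not asked for the further year, so the mismatch does not concern them while that status holds.

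**Could the further year fall inside the study's duration?** No. Section 5.6.1 ends the study at Visit 15, and both variants of Section 4.2 count the year from completion of the trial. The year lies outside the study by the protocol's own terms.

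**Inputs (Appendix 7, days after Visit 9):**
- Visit 9, first extension infusion: day 0
- Visit 12, last infusion: day 180
- Visit 15, end of study: day 365
- one year taken as 365 days

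**From the first extension infusion:**
- Section 10.2: 365 − 0 = 365 days
- Section 4.2: 365 + 365 = 730 days at least
- Difference: 730 − 365 = 365 days at least

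**From the last infusion:**
- Section 10.2: 365 − 180 = 185 days
- Section 4.2: 185 + 365 = 550 days at least
- Difference: 550 − 185 = 365 days at least

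The difference is the same from either starting point and for both variants, because each adds the same year. The figures give the size of the gap in wording; they do not measure protection lost.

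**The case against.** The strongest reply is that Section 10.2 sets no rule of its own. It refers to a contraception requirement, which is defined in Section 4.2. Eligibility is checked at Visits 8A and 9 (Tables 6-1 and 6-2), and under Section 10.3 the investigator signs to follow the whole protocol. No girl can properly enter on the shorter commitment, and an investigator would have to overlook the eligibility criteria to be misled.

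Much of this stands: the operative rule is intact. But the words after that reference limit how long the girl agrees to comply, and that limit is too short. The risk sentence contains no reference to the requirement, and it too stops at the end of the study. An investigator bound by both sections has been given two different periods.

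A second reply is that what girls are actually told is set by the consent form, which may be correct. That also stands. A reader might infer that girls were asked to agree to too short a period, or were left unprotected for a year. The documents do not support either inference: the form is not available and Section 4.2 demands the longer commitment.

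A reader might also infer a defect in follow-up after Visit 15. That is a different question. The follow-up schedule would be the same before and after this correction, and Section 7.4 requires each pregnancy occurring after consent to be reported, with no end date given.

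**Conclusion.** Section 10.2 is wrong as written, and the severity is minor. It states the fetal-risk information and the contraception agreement for a period at least one year shorter than both variants of Section 4.2, and it attaches the judgement of reliable compliance to that shorter period.

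The count in days assumes the planned visit timing of Appendix 7 and a year of 365 days; the finding of at least one year does not depend on the visit timing. The documents do not give the number of girls concerned. No effect on actual consent is shown, and no analysis or statistical figure is affected.

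**What to change.** In Section 10.2, change two sentences.

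1. Extend the risk sentence to a pregnancy occurring in the study or within at least one year of completing it.
2. Extend the agreement to the same period, with an explicit reference to Section 4.2 so that the site's own variant applies.

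The entry judgement then needs no separate edit, because it will rest on the corrected period. Check that the proposed consent and assent forms give the same period.

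The cost is two wording changes in a protocol amendment and a check of the forms. No visit, procedure, eligibility criterion or analysis changes. If a form turns out to carry the shorter period, it would also have to be revised and go back to the ethics committee.

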10.3 Responsibilities of the investigator and IRB/IEC

Before initiating a trial, the investigator/institution must obtain approval/favorable opinion from the Institutional Review Board/Independent Ethics Committee (IRB/IEC) for the trial protocol, written informed consent form, consent form updates, subject recruitment procedures (e.g., advertisements) and any other written information to be provided to patients. Prior to study start, the investigator is required to sign a protocol signature page confirming his/her agreement to conduct the study in accordance with these documents and all of the instructions and procedures found in this protocol and to give access to all relevant data and records to Novartis monitors, auditors, Novartis Clinical Quality Assurance representatives, designated agents of Novartis, IRBs/IECs, and regulatory authorities as required. If an inspection of the clinical site is requested by a regulatory authority, the investigator must inform Novartis immediately that this request has been made.

10.4 Publication of study protocol and results

The key design elements of this protocol will be posted in a publicly accessible database such as clinicaltrials.gov. In addition, upon study completion and finalization of the study report the results of this trial will be either submitted for publication and/or posted in a publicly accessible database of clinical trial results.

10.5 Quality Control and Quality Assurance

[figure not shown]
Novartis maintains a robust Quality Management (QM) system that includes all activities involved in quality assurance and quality control, including the assignment of roles and responsibilities, the reporting of results, and the documentation of actions and escalation of issues identified during the review of quality metrics, incidents, audits and inspections.

Audits of investigator sites, vendors, and Novartis systems are performed by Novartis Pharma Auditing and Compliance Quality Assurance (CQA), a group independent from those involved in conducting, monitoring or performing quality control of the clinical trial. The clinical audit process uses a knowledge/risk based approach.

Audits are conducted to assess GCP compliance with global and local regulatory requirements, protocols and internal SOPs, and are performed according to written Novartis processes.

11 Protocol adherence

This protocol defines the study objectives, the study procedures and the data to be collected on study participants. Additional assessments required to ensure safety of patients/subjects should be administered as deemed necessary on a case by case basis. Under no circumstances is an investigator allowed to collect additional data or conduct any additional procedures for any research related purpose involving any investigational drugs under the protocol.

Investigators ascertain they will apply due diligence to avoid protocol deviations. If the investigator feels a protocol deviation would improve the conduct of the study this must be considered a protocol amendment, and unless such an amendment is agreed upon by Novartis and approved by the IRB/IEC it cannot be implemented.

13 Appendix 1: Clinically notable laboratory values and vital signs

Table 13-1 Clinical notable criteria for selected laboratory tests

Laboratory parameter	Units	Age/gender range	Normal range	Criteria for clinically significant change
Systolic Blood Pressure	mmHg	< 12 yrs	(70.0, 125.0)	If within the normal range at baseline, a value outside of normal range along with at least a 20 unit change
		12 yrs/male	(90.0, 127.0)	If within the normal range at baseline, a value outside of normal range along with at least a 20 unit change
		13 yrs/male	(90.0, 130.0)	If within the normal range at baseline, a value outside of normal range along with at least a 20 unit change
		14 yrs/male	(90.0, 132.0)	If within the normal range at baseline, a value outside of normal range along with at least a 20 unit change
		15 yrs/male	(90.0, 135.0)	If within the normal range at baseline, a value outside of normal range along with at least a 20 unit change
		16 yrs/male	(90.0, 138.0)	If within the normal range at baseline, a value outside of normal range along with at least a 20 unit change
		17 – 20 yrs/ male	(90.0, 140.0)	If within the normal range at baseline, a value outside of normal range along with at least a 20 unit change
		12 yrs/female	(90.0, 126.0)	If within the normal range at baseline, a value outside of normal range along with at least a 20 unit change
		13 yrs/female	(90.0, 128.0)	If within the normal range at baseline, a value outside of normal range along with at least a 20 unit change
		14 yrs/female	(90.0, 130.0)	If within the normal range at baseline, a value outside of normal range along with at least a 20 unit change

Laboratory parameter	Units	Age/gender range	Normal range	Criteria for clinically significant change
		15 yrs/female	(90.0, 131.0)	If within the normal range at baseline, a value outside of normal range along with at least a 20 unit change
		16 yrs/female	(90.0, 132.0)	If within the normal range at baseline, a value outside of normal range along with at least a 20 unit change
		17-20 yrs/female	(90.0, 132.0)	If within the normal range at baseline, a value outside of normal range along with at least a 20 unit change
Diastolic Blood Pressure	mmHg	< 12 yrs	(40.0, 85.0)	If within the normal range at baseline, a value outside of normal range along with at least a 15 unit change
		12 yrs/male	(50.0, 83.0)	If within the normal range at baseline, a value outside of normal range along with at least a 15 unit change
		13 yrs/male	(50.0, 84.0)	If within the normal range at baseline, a value outside of normal range along with at least a 15 unit change
		14 yrs/male	(50.0, 85.0)	If within the normal range at baseline, a value outside of normal range along with at least a 15 unit change
		15 yrs/male	(50.0, 86.0)	If within the normal range at baseline, a value outside of normal range along with at least a 15 unit change
		16 yrs/male	(50.0, 87.0)	If within the normal range at baseline, a value outside of normal range along with at least a 15 unit change
		17-20 yrs/male	(50.0, 89.0)	If within the normal range at baseline, a value outside of normal range along with at least a 15 unit change
		12 yrs/female	(50.0, 82.0)	If within the normal range at baseline, a value outside of normal range along with at least a 15 unit change
		13 yrs/female	(50.0, 84.0)	If within the normal range at baseline, a value outside of normal range along with at least a 15 unit change

Laboratory parameter	Units	Age/gender range	Normal range	Criteria for clinically significant change
		14 yrs/female	(50.0, 85.0)	If within the normal range at baseline, a value outside of normal range along with at least a 15 unit change
		15 yrs/female	(50.0, 86.0)	If within the normal range at baseline, a value outside of normal range along with at least a 15 unit change
		16 yrs/female	(50.0, 86.0)	If within the normal range at baseline, a value outside of normal range along with at least a 15 unit change
		17-20 yrs/ female	(50.0, 86.0)	If within the normal range at baseline, a value outside of normal range along with at least a 15 unit change
Heart Rate	bpm	< 12 yrs	(70.0, 130.0)	If within the normal range at baseline, a value outside of normal range along with at least a 15 unit change
		≥ 12 yrs	(50.0, 120.0)	If within the normal range at baseline, a value outside of normal range along with at least a 15 unit change
Clinical Chemistry				
Blood Urea Nitrogen (serum urea)	mg/dL	≤ 20 yrs	(4.0, 24.0)	Outside the normal range
Calcium	mg/dl	> 2 - 20 yrs	(8.4, 10.3)	Outside the normal range
Chloride	mEq/L	≤ 20 yrs	(94.0, 112.0)	Outside the normal range
Creatinine	mg/dl	5 - 7 yrs/ Female	(0.2, 0.5)	Outside the normal range
		> 7- 10 yrs/ Female	(0.2, 0.6)	Outside the normal range
		> 10 - 13 yrs/ Female	(0.3, 0.7)	Outside the normal range
		> 13 - 16 yrs/ Female	(0.4, 0.8)	Outside the normal range
		> 16 - 20 yrs/ Female	(0.5, 0.9)	Outside the normal range
		5 - 7 yrs/ Male	(0.2, 0.5)	Outside the normal range
		> 7- 10 yrs/ Male	(0.3, 0.6)	Outside the normal range
		> 10 - 13 yrs/ Male	(0.3, 0.7)	Outside the normal range
> 13 - 16 yrs/ Male	(0.4, 0.8)	Outside the normal range		

Laboratory parameter	Units	Age/gender range	Normal range	Criteria for clinically significant change		
Magnesium	mg/dl	> 16 - 20 yrs/ Male	(0.5, 0.9)	Outside the normal range		
		5 - 7 yrs/ Female	(1.7, 2.2)	Clinically significantly low, if < 1.0 mg/dL		
		> 7- 10 yrs/ Female	(1.6, 2.2)	Clinically significantly low, if < 1.0 mg/dL		
		> 10 - 13 yrs/ Female	(1.6, 2.2)	Clinically significantly low, if < 1.0 mg/dL		
		> 13 - 16 yrs/ Female	(1.6, 2.3)	Clinically significantly low, if < 1.0 mg/dL		
		> 16 - 20 yrs/ Female	(1.5, 2.2)	Clinically significantly low, if < 1.0 mg/dL		
		5 - 7 yrs/ Male	(1.7, 2.4)	Clinically significantly low, if < 1.0 mg/dL		
		> 7- 10 yrs/ Male	(1.6, 2.2)	Clinically significantly low, if < 1.0 mg/dL		
		> 10 - 13 yrs/ Male	(1.6, 2.2)	Clinically significantly low, if < 1.0 mg/dL		
		> 13 - 16 yrs/ Male	(1.6, 2.3)	Clinically significantly low, if < 1.0 mg/dL		
		> 16 - 20 yrs/ Male	(1.5, 2.2)	Clinically significantly low, if < 1.0 mg/dL		
		Potassium	mEq/L	> 1 - 20 yrs	(3.4, 5.4)	Outside the normal range
Phosphorus	mg/dl	5 - 10 yrs	(3.2, 6.1)	Outside the normal range		
		> 10 - 15 yrs	(3.1, 6.0)	Outside the normal range		
		> 15 - 20 yrs	(2.2, 5.1)	Outside the normal range		
		Sodium	mEq/L	≤ 20 yrs	(132.0, 147.0)	Outside the normal range
ALT	U/L	5- 20 yrs	(6 , 200)	Outside the normal range		
AST	U/L	5- 20 yrs	(10 , 200)	Outside the normal range		
Alkaline Phosphatase	U/L	5- 20 yrs	(51 , 315)	Outside the normal range		
Albumin	g/dL	5- 20 yrs	(2.9 – 4.7)	Outside the normal range		
GGT	U/L	5 – 10 yrs/ Female	(0, 24)	Outside the normal range		
		10 – 18 yrs/ Female	(0, 33)	Outside the normal range		
		18 – 20 yrs/ Female	(4, 49)	Outside the normal range		
		5 – 10 yrs/ Male	(0, 24)	Outside the normal range		
		10 – 18 yrs/ Male	(0, 51)	Outside the normal range		
		18 – 20 yrs/ Male	(10, 61)	Outside the normal range		
		Total bilirubin	µmol/L	5 - 20 yrs	(3, 21)	Outside the normal range
		Hematology				

Laboratory parameter	Units	Age/gender range	Normal range	Criteria for clinically significant change
Hemoglobin	g/dl	5 - 12 yrs/ Female	(11.2, 15.5)	Outside the normal range
		> 12 - 20 yrs/ Female	(11.6, 16.4)	Outside the normal range
		5 - 12 yrs/ Male	(11.2, 15.5)	Outside the normal range
		> 12 - 20 yrs/ Male	(12.7, 18.1)	Outside the normal range
Hematocrit	%	5- 6 yrs/ Female	(35.0, 44.0)	Outside the normal range
		> 6 - 12 yrs/ Female	(34.0, 44.0)	Outside the normal range
		> 12 - 20 yrs/ Female	(34.0, 48.0)	Outside the normal range
		5 - 6 yrs/ Male	(33.0, 43.0)	Outside the normal range
		> 6 - 12 yrs/ Male	(34.0, 44.0)	Outside the normal range
		> 12 - 20 yrs/ Male	(39.0, 54.0)	Outside the normal range
RBC	10 ⁶ /uL	> 3 - 6 yrs/ Female	(4.1, 5.2)	Outside the normal range
		> 6 - 12 yrs/ Female	(3.7, 6.0)	Outside the normal range
		> 12 - 20 yrs/ Female	(4.1, 5.6)	Outside the normal range
		5- 6 yrs/ Male	(4.1, 5.3)	Outside the normal range
		> 6 - 12 yrs/ Male	(3.7, 6.0)	Outside the normal range
		> 12 - 20 yrs/ Male	(4.5, 6.4)	Outside the normal range
WBC	10 ³ /uL	5- 6 yrs	(4.00, 12.00)	Outside the normal range
		> 6 - 12 yrs	(4.35, 13.65)	Outside the normal range
		> 12 - 20 yrs	(4.35, 13.15)	Outside the normal range
Lymphocytes	10 ³ /uL	5- 6 yrs/ Female	(1.50, 8.00)	Outside the normal range
		> 6 - 12 yrs/ Female	(1.15, 6.65)	Outside the normal range
		> 12 - 20 yrs/ Female	(0.95, 5.25)	Outside the normal range
		5- 6 yrs/ Male	(1.50, 8.00)	Outside the normal range
		> 6 - 12 yrs/ Male	(1.15, 6.65)	Outside the normal range
Neutrophils	10 ³ /uL	> 12 - 20 yrs/ Male	(0.95, 5.25)	Outside the normal range
		5- 6 yrs/ Female	(1.00, 9.00)	Outside the normal range

Laboratory parameter	Units	Age/gender range	Normal range	Criteria for clinically significant change
		> 6 - 12 yrs/ Female	(1.35, 8.15)	Outside the normal range
		> 12 - 20 yrs/ Female	(1.65, 8.15)	Outside the normal range
		5- 6 yrs/ Male	(1.35, 8.65)	Outside the normal range
		> 6 - 12 yrs/ Male	(1.35, 8.65)	Outside the normal range
		> 12 - 20 yrs/ Male	(1.65, 8.15)	Outside the normal range
Eosinophils	10 ³ /uL	≤ 20 yrs	(0.00, 0.57)	Outside the normal range
MCV	fL	5 – 6 yrs/ Female	(74, 89)	Outside the normal range
		6 – 12 yrs/ Female	(76, 93)	Outside the normal range
		12 – 20 yrs/ Female	(79, 98)	Outside the normal range
		5 – 6 yrs/ Male	(74, 89)	Outside the normal range
		6 – 12 yrs/ Male	(76, 93)	Outside the normal range
		12 – 20 yrs/ Male	(79, 96)	Outside the normal range
MCHC	g/L	5 - 20 yrs	(310, 380)	Outside the normal range
RBC Morph		5 - 20 yrs	Normal	Outside the normal range
Urinalysis		5 – 20 yrs	Normal	Outside the normal range

Lab normal ranges provided by Covance Labs

14 Appendix 2: Tanner Staging

Male patients - Development of external genitalia

Stage 1: Pre-adolescent. Testes, scrotum, and penis are of about the same size and proportion as in early childhood.

Stage 2: The scrotum and testes have enlarged and there is a change in the texture of the scrotal skin.

Stage 3: Growth of the penis has occurred, at first mainly in length; these has been further growth of testes and scrotum

Stage 4: Penis further enlarged in length and breadth with development of glans. Testes and scrotum further enlarged. There is also further darkening of the scrotal skin

Stage 5: Genitalia adult in size and shape

Female patients - Breast development

Stage 1: Pre-adolescent; elevation of papilla only.

Stage 2: Breast bud stage; elevation of breast and papilla as a small mound, enlargement of areola diameter.

Stage 3: Further enlargement of breast and areola, with no separation of their contours.

Stage 4: Projection of areola and papilla to form a secondary mound above the level of the breast.

Stage 5: Mature stage; projection of papilla only, due to recession of the areola to the general contour of the breast.

The girls will be asked at each visit if they had begun to menstruate.

Male and female patients - Pubic hair

Stage 1: Pre-adolescent (can see velus hair similar to abdominal wall).

Stage 2: Sparse growth of long, slightly pigmented, downy hair, straight or only slightly curled, appearing chiefly along the labia or the base of the penis.

Stage 3: Considerably darker, coarser and more curled hair. The hair spreads sparsely over the junction of the pubes.

Stage 4: Hair is now adult in type, but the area covered by is still considerably smaller than in most adults. There is no spread to the medial surface of thighs.

Stage 5: Adult in quantity and type, distributed as an inverse triangle of the classically feminine pattern. Spread to the medial surface of the thighs (about age 15 years).

([Marshall and Tanner 1970](#); [Marshall and Tanner 1969](#))

15 Appendix 3: Faces Pain Scale

© 2001 International Association for Study of Pain

Faces Pain Scale – Revised (FPS-R)

From Pediatric Pain Sourcebook, www.painsourcebook.ca
Version: 7 Aug 2007 CL von Baeyer

[figure not shown]
[figure not shown]
In the following instructions, say "hurt" or "pain," whichever seems right for a particular child.

"These faces show how much something can hurt. This face [point to left-most face] shows no pain. The faces show more and more pain [point to each from left to right] up to this one [point to right-most face] – it shows very much pain. Point to the face that shows how much you hurt [right now]."

[figure not shown]
Score the chosen face 0, 2, 4, 6, 8, or 10, counting left to right, so '0' = 'no pain' and '10' = 'very much pain.' Do not use words like 'happy' and 'sad'. This scale is intended to measure how children feel inside, not how their face looks.

[figure not shown]
0 2 4 6 8 10

[figure not shown]

PedsQL 2

18 Appendix 6: Other subtypes of osteoporosis in children

Allowed	Disallowed
Cerebral palsy	Leukemia or lymphoma
Becker's dystrophy	Solid tumors
Diabetes mellitus	Thalassemia
Celiac disease	Mastocytosis
Cystic fibrosis	Hypogonadism
	Growth Hormone deficiency
	Hyperthyroidism
	Vitamin D deficiency
	Anorexia nervosa
	Chronic kidney disease
	Secondary hyperparathyroidism
	Organ transplant recipient
	Biliary atresia
	Female athletic triad
	Spinal cord injury

19 Appendix 7: Amount of blood to-be Drawn

Only the laboratory samples which apply to the Visits in the Extension study are included.

Period								
Visit	8A	9	10	11 ^T	12	13	14 ^T	15/EOS and TD and/or PSW
Day	-60 to -30	0	10 days after V9	90 days after V9	180 days after V9	190 days after V9	270 days after V9	365 days after V9
Week	-8 to -4			12	26		39	52
Central Laboratory - All Patients								
Hematology	3 mL				3 mL			3 mL
Chemistry	3.5 ml [6 mL (Australia only)]				3.5 mL			3.5 mL [6 mL (Australia only)]
Renal & Ca monitoring ¹			3.5 mL			3.5 mL		
Serum pregnancy ²	2.5mL							2.5mL
Specialized serum bone-markers		3 mL ³			3 mL			3 mL
Vitamin D	2.5 mL							2.5 mL
Local Laboratory - All Patients								
Serum creatinine		2.5 mL						
Serum ionized calcium		2.5 mL						
TOTALS	14 mL [16.5mL (Australia only)]	8 mL	3.5mL	-	9.5mL	3.5mL	-	14.5 mL [17.0mL (Australia only)]
¹ Serum creatinine, urea, electrolytes, calcium, magnesium, phosphorus only								
² Only in girls of child bearing potential								
³ Only repeated in Group 1 if more than 30 days after Visit 8 of the Core study
